The purpose of the first interim analysis is to allow early stopping of the study for futility, assessing safety of the treatment, and potentially adjusting the sample size. The trial may be stopped for futility at the interim analysis or the sample size of the study may be adjusted up to ensure enough power to detect the treatment effect (section 14). The first interim analysis is planned to be performed when 30 subjects complete (half of the pre-defined sample size for primary endpoint, 15 subjects for each treatment group) the Month 6 visit. A fraction of alpha (0.0001) will be spent at the first interim analysis and accounted for in the overall type I error rate. Even if the value of test-statistics exceeds the efficacy boundary, the trial will not be stopped for efficacy. NOTE: For simplicity, 30 subjects complete the Month 6 visit and balanced arms are assumed to demonstrate statistical analyses in this document.

The futility of the study at the first interim analysis will be determined by calculating the conditional power (CP) based on observed trend at interim.

If the CP is  $< CP_{min}$ , the study will be stopped for futility. If the CP is between  $CP_{min}$  and 60%, the sample size will be adjusted up to make CP equal to 60%. The  $CP_{min}$  is the pre-specified lower limit of conditional power and will be specified in the DMC SAP before the 1st interim analysis. The analysis based on the adjusted number of subjects will be used for the final analysis on primary endpoint (i.e. second interim analysis in the study). The study will continue with the original planned sample size if CP is 60% or above.

The CP at the first interim analysis, assuming that the data that will be observed after the first interim analysis will follow the same distribution as seen at interim and the CHW weighted test statistic  $Z_{CHW}$  (Cui et al., 1999) as the final test statistic for second interim analysis (also see definition below), will be determined by the following formulae:

$$CP = P\left(Z_2 > \frac{Z_{1-\alpha} - w_1 Z_1}{w_2}\right)$$

$$= 1 - \Phi \left( \frac{Z_{1-\alpha} - w_1 Z_1 - \frac{\Delta}{\sqrt{\frac{2\bar{P}(1-\bar{P})}{n_2}}}}{w_2} \right)$$

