Where  $Z_1$  and  $Z_2$  are the Z test statistics from the first interim stage (from beginning to first interim analysis) and second interim stage (from first interim analysis to second interim analysis) respectively,  $w_1 = w_2 = \sqrt{\frac{1}{2}}$ ,  $n_2$  is the sample size at the second interim stage per treatment group,  $\Phi(\cdot)$  is cumulative standard normal distribution function,  $\Delta = \hat{\Pi}_{Placebo} - \hat{\Pi}_{Cinryze}$ , and  $Z_i$  ( $i = 1, 2$ ) is calculated as below:

$$Z_i = \frac{\hat{\Pi}_{Placebo} - \hat{\Pi}_{Cinryze}}{\sqrt{\bar{P}(1-\bar{P})\left(\frac{1}{n_{i,Placebo}} + \frac{1}{n_{i,Cinryze}}\right)}}$$

$\hat{\Pi}_{Placebo}$  and  $\hat{\Pi}_{Cinryze}$  are estimated proportions of new or worsening TG at 6 months post treatment at the first interim stage for the Placebo group and CINRYZE group, respectively.

The pooled proportion  $\bar{P} = \frac{n_{i,Placebo}\hat{\Pi}_{Placebo} + n_{i,Cinryze}\hat{\Pi}_{Cinryze}}{n_{i,Placebo} + n_{i,Cinryze}}$ , where  $n_{i,Placebo}$ ,  $n_{i,Cinryze}$  ( $i = 1, 2$ ) are numbers of subjects for the Placebo group and the CINRYZE group at first or second interim stage, respectively. The pre-defined sample size for second interim stage is:

$$n_{2,Placebo} = n_{2,Cinryze} = n_2 = 15$$

If  $CP(n_2 = 15) < CP_{min}$ , the futility of the study will be claimed.

If  $CP_{min} \leq CP(n_2 = 15) < 60\%$ ,  $n_2$  will be adjusted to  $n_2^*$  satisfy  $CP(n_2^*) \geq 60\%$ .

If  $CP(n_2 = 15) \geq 60\%$ , study will continue without sample size adjustment.

The second interim analysis serves as the final analysis for the primary endpoint. The purpose of the second interim analysis is to allow early stopping of the study for futility or for claiming of efficacy based on new or worsening TG at 6 months. This analysis will be done using the FAS when a required number of subjects (based on the sample size adjustment of first interim analysis) complete the Month 6 TG assessments. If the result of the final analysis for primary endpoint analysis is statistically significant at 0.0249, the primary null hypothesis will be rejected. The difference between treatments will be evaluated by using the CHW weighted test

statistic (Cui et al., 1999). The test statistic  $Z_{CHW}$  at the second interim analysis for TG will be derived based on CHW method, i.e.,

$$Z_{CHW} = \sqrt{\frac{15}{30}}Z_1 + \sqrt{\frac{15}{30}}Z_2 \quad (\text{Formulae 1})$$

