where  $Z_1$  is the normalized test statistic at first interim stage, and  $Z_2$  is the normalized test statistic for incremental sample size  $n_2^*$  for second interim stage after the sample size adjustment. If the number of TG events exceeds 5 for all four cells in the contingency table of treatment versus TG event,  $Z_i$  ( $i = 1, 2$ ) will be obtained using normal approximation, otherwise  $Z_i$  ( $i = 1, 2$ ) will be calculated from p-value of Fisher's Exact test as (Lechmacher et al., 1999):

$$Z_i = \Phi^{-1}(1 - p_i)$$

where  $\Phi^{-1}(.)$  is the function to return a quantile from the standard normal distribution,  $p_1$  is the p-value from Fisher's Exact test for the first interim stage, and  $p_2$  is the p-value from Fisher's Exact test for incremental sample size  $n_2^*$  for second interim stage after the sample size adjustment.

If  $Z_{CHW} \geq Z_{1-\alpha/2, 49}$  (equivalent to the p-value from the test  $\leq 0.0249$ ), the null hypothesis will be rejected. Otherwise, the futility of the study will be claimed.

The following sensitivity analyses will be conducted for TG assessment by the granular score for the FAS and then TG assessment by the standard score and the granular score for Per-Protocol Analysis Set-1:

- Sensitivity analysis 1: Primary analysis will be repeated based on Month 6 TG assessment by granular score for the Full Analysis Set
- Sensitivity analysis 2: Primary analysis will be repeated based on Month 6 TG assessment by standard score for the Per Protocol Analysis Set-1
- Sensitivity analysis 3: Primary analysis will be repeated based on Month 6 TG assessment by granular score for the Per Protocol Analysis Set-1

The TG assessment by the granular score at 6 months is defined as the following:

- Worsening TG is defined as an increase of 6.25 in the glomerular capillary double contour percentage between qualifying biopsy and 6-month biopsy.

- New TG is defined by granular Banff (based on 2013 Banff criteria) cg 0 score in the qualifying biopsy and granular Banff (based on 2013 Banff criteria) cg score of greater than 0 in the 6-month biopsy.

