In order to demonstrate the stability of the primary analysis method, sensitivity analyses will be performed at the point of final analysis of primary endpoint (i.e. second interim analysis for study) by using multiple imputation (MI) assuming missing at random (MAR) to assign missing endpoint and/or combined with Cochran–Mantel–Haenszel (CMH) test for treatment effect. The CMH model will assess the treatment effect controlling for (1) donor characteristic (living vs deceased), (2) baseline AMR severity (severe vs mild to moderate) and possibly (3) time to onset of qualifying AMR from current transplant (>100 days vs  $\leq$ 100 days) if degree of freedom allows. Sensitivity analyses defined below will be based on the FAS.

	Statistical Test	Logic to assign the missing TG assessment at 6 months
Primary analysis model	Fisher's Exact with CHW weighted test	If no TG assessment at 6 months, assign as failure.
Sensitivity analysis 4	Fisher's Exact with CHW weighted test	If no TG assessment at 6 months, perform MI.
Sensitivity analysis 5	CMH with CHW weighted test	If no TG assessment at 6 months, assign as failure.
Sensitivity analysis 6	CMH with CHW weighted test	If no TG assessment at 6 months, perform MI

For multiple imputation, a monotone missing pattern will be assumed and logistic regression model will be utilized. The imputation seed will be 83789524 and number of imputations will be set as 100. The logistic regression model may contain the following factors (descending order by importance) to impute the missing TG assessment at 6 months:

- (1) Treatment group (CINRYZE vs placebo);
- (2) AMR severity at baseline (severe vs mild/ moderate);
- (3) Donor characteristics (living donor vs deceased donor);
- (4) Normalized eGFR change ( $\Delta_{eGFR}$ ).  $\Delta_{eGFR} = \frac{eGFR_{baseline} - eGFR_{last}}{T}$ , where   
 $eGFR_{baseline}$  is the last eGFR results prior to the first dose of investigational product,  $eGFR_{last}$  is the last eGFR result before or at Month 6 or early discontinuation visit, and T = (last eGFR assessment date – Date of first dose + 1)/30.25;
- (5) Resolution of qualifying AMR (Resolved by 6 months /early discontinuation vs unresolved by 6 months/early discontinuation);

(6) AMR free time in months, which defines as (date of Month 6 or early discontinuation visit – Date of first dose +1 – number of days with AMR)/30.25

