## 14. INTERIM ANALYSIS

The study is designed to have 2 analyses (interim and final analyses) assessing the primary endpoint of new or worsening TG at 6 months after initiation of treatment. In addition, there will be 3 analyses (2 interim analyses plus 1 final analysis) assessing proportions of subjects with all-cause graft failure, at approximately 50% (~26 events), 75% (~39 events), and 100% (~51 events) of the study information. An independent DMC will review the data on 4 interim analyses during the course of the study.

The first interim analysis is after 30 subjects complete the Month 6 TG assessment. The purpose of the first interim analysis is to allow early stopping of the study for futility, assessing safety of the treatment, and potentially adjusting the sample size. An alpha level of 0.0001 will be spent at first interim analysis based on the Haybittle-Peto approach. The trial will not be stopped even if the value of test-statistics exceeds the efficacy. The futility of the study at the first interim analysis will be determined by calculating the conditional power (CP) based on observed trend at interim. If the CP is  $\leq CP_{min}$ , the study will be stopped for futility. If the CP is between  $CP_{min}$  and 60%, the sample size will be adjusted up to make CP equal to 60%. The study will continue without sample size adjustment if CP is 60% or above. The  $CP_{min}$  is the pre-specified lower limit of conditional power and will be specified in the DMC SAP before the 1st interim analysis. The details for calculating CP can be found in [Section 10.1](#).

The final analysis for the primary endpoint (i.e. second interim analysis for the study) will be done after the required number of subjects (based on the first interim analysis sample size re-estimation) complete the Month 6 TG assessment. The purpose of the second interim analysis for the study is to allow early stopping of the study for futility or for claiming of efficacy based on new or worsening TG at 6 months. CHW method ([Cui et al., 1999](#)) will be used to evaluate the efficacy by using a one-sided alpha significance level of 0.0249. Details of analysis can be found in [Section 10.1](#).

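### Conditional power in SAP 10.1 is built on normal Z statistics, but the planned CHW test nearly always uses Fisher-based ones, so a stated 60% is usually well above the test's real chance of rejecting

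*SAP*

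**What the plan says.** SAP 10.1 bases futility and sample size re-estimation at the first interim analysis (30 subjects, 15 per arm) on CP under the observed rates. The CHW statistic is taken "as the final test statistic for second interim analysis (also see definition below".

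- **In the CP.** Z1 and Z2 "are the Z test statistics from the first interim stage (from beginning to first interim analysis) and second interim stage", and both are defined by the pooled-variance normal formula. No exception is given.
- **In the test.** "If the number of TG events exceeds 5 for all four cells in the contingency table of treatment versus TG event", the stage's Z comes from the normal approximation. Otherwise it "will be calculated from p-value of Fisher's Exact test as" Φ⁻¹(1 − p).
- **In the table of analysis models.** The primary model is listed as "Fisher's Exact with CHW weighted test", with no switching rule.
- **The decisions.** Below CPmin the study stops for futility. Between CPmin and 60%, "the sample size will be adjusted up to make CP equal to 60" per cent. At 60% or more, the "study will continue without sample size adjustment".

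SAP 14 adds nothing of its own: "The details for calculating CP can be found in" Section 10.1.

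**The concern.** CP is meant to be the probability that the planned test rejects, given the interim data. Here it is computed for a different test. With small cells, a Z from Fisher's p-value is clearly smaller than the pooled normal Z. The CP therefore starts from too large a Z1 and assumes a more powerful second stage than the plan provides.

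Three decisions hang on this number: futility, no adjustment, and the re-estimated second-stage size n2*. If the CP is too high, the rule can leave the size at 15 per arm, or raise it too little, while the test's real chance of success is far below the 60% target.

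**Working it through.** **Inputs.** From SAP 10.1: n1 = 15 per arm, default n2 = 15 per arm, w1 = w2 = √½, final one-sided level 0.0249 (z = 1.962), stage 2 rates equal to the interim rates. From SAP 2.5: design rates 50% placebo and 10% CINRYZE. Two assumptions are needed: α = 0.0249 in the CP formula, which prints only α; and a one-sided Fisher p, which fits the one-sided hypothesis and the right-sided p in the Appendix 1 code.

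**The plan's own figure.** SAP 2.5 gives at least 90% power with 30 per arm. This reproduces: 94.3% by the normal formula and 91.4% for a single one-sided Fisher test. For CHW at 15 + 15 per arm, power at 50% v 10% is 95.1% with normal Z throughout and 85.1% with the switching rule.

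**How often Fisher applies at stage 1.** With 15 per arm, all four cells exceed 5 only if both arms have 6 to 9 events. The Fisher branch therefore applies with probability 99.8% at 50%/10%, 96% at 50%/20%, 81% at 50%/30% and 51% at 50%/50%. Among the tables that keep the normal Z, the highest CP at n2 = 15 is 28% (9 v 6). So every no-adjustment decision comes from a table where the test would use a Fisher Z1.

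**Formulas.**

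- Stated CP: 1 − Φ[(1.962 − w1·Z1)/w2 − Δ/√(2P(1−P)/n2)], with the pooled normal Z1.
- Planned test: enumerate all stage 2 tables at the interim rates. Take each stage's Z by the switching rule, and reject if √½·Z1 + √½·Z2 ≥ 1.962.

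**Example, 7 v 3.** Δ = 4/15 and P = 10/30, so Z1 = 0.2667/√(0.2222 × 2/15) = 1.549. The drift at n2 = 15 is also 1.549. Then 1.962/0.7071 − 1.549 = 1.225, and CP = 1 − Φ(1.225 − 1.549) = 63%. The planned test has Z1 = 1.162, so it needs Z2 ≥ 2.774 − 1.162 = 1.612, usually again on the Fisher scale. Enumeration gives 31%.

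| Events, placebo v CINRYZE | Z1, CP v test | CP at n2 = 15, stated v planned test | All-normal enumeration | n2* per arm, stated rule v planned test | Planned test's CP at stated n2* |
|---|---|---|---|---|---|
| 8 v 4 | 1.491 v 1.118 | 58% v 29% | 59% | 16 v 25 | 33% |
| 7 v 3 | 1.549 v 1.162 | 63% v 31% | 62% | 15 v 26 | 31% |
| 5 v 2 | 1.295 v 0.860 | 43% v 15% | 43% | 27 v 44 | 34% |
| 6 v 3 | 1.195 v 0.794 | 35% v 11% | 35% | 36 v 52 | 44% |

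The all-normal column matches the stated CP, so the gap comes from the Fisher switch and not from the normal approximation as such.

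**Over all interim tables.** The probability that the stated CP says no adjustment while the planned test's CP is below 60% is 13% at 50%/10%, 19% at 50%/20% and 14% at 50%/30%. With the planned test's CP below 50%, it is 10%, 10% and 5%. Examples at n2 = 15 are 3 v 0 (81% v 35%), 5 v 1 (81% v 47%) and 6 v 2 (70% v 40%). In the zone where the size is raised, the planned test's mean CP at the stated n2* is 35–37%, 39–41% and 40–43% for the same three scenarios. CPmin is not given in the SAP; this assumes 10–30%, with n2* up to 120.

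**Exceptions.** Where all stage 1 cells exceed 5 and n2* is large, the two agree: 8 v 6 and 9 v 7 at n2 = 148 give 60.1% v 60.4%, and 9 v 6 at n2 = 47 gives 60.3% v 58.5%.

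**Sensitivity.** α = 0.025 moves CP at n2 = 15 by at most 0.1 point. A two-sided Fisher p would lower the planned test's CP for the four tables to 10%, 11%, 2% and 2%, so the one-sided reading is the favourable one.

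**The case against.** **The study is over.** SAP 17 records a stop after the first interim analysis, so there will be no second stage and no CHW test, and the output list in SAP 20 has no CP table. This stands as a limit on consequence. So does the fact that the interim analyses followed the DMC SAP v3.0, which is not available here: nothing shows which formula was used. It does not make the SAP's text consistent, and SAP 17 gives the re-estimated size and the futility criteria as grounds for the stop.

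**The reference to a definition below may mean the Fisher-based Z.** The pooled formula is printed explicitly for the CP's Z1 and Z2, which weighs against this. Even with the Fisher Z1 in the CP, the second stage stays normal: 7 v 3 at n2 = 15 gives 47.5% against 31%. For n2* this reading comes close (25, 22, 43 and 53 against 25, 26, 44 and 52) but still falls short for 7 v 3.

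**The CP formula used here is not the printed one.** The first line of the SAP's formula holds for any Z1 and Z2. The figures above evaluate it with the section's own pooled Z. The second line, as extracted, also divides the drift by w2, which does not follow from the first. Taken literally, it gives about 80%, 83%, 64% and 54% for the four tables and widens the gap. It may be an extraction artefact, and no result above relies on it.

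**The practical cost is modest.** This partly stands. The plan randomises 56 per arm anyway, leaving 56 − 15 = 41 for stage 2, so 25 or 26 per arm means only a later analysis. For 5 v 2 and 6 v 3 the totals are 15 + 44 = 59 and 15 + 52 = 67 per arm, above 56. At the design rates the stated CP reaches 60% in 86% of interims, so the 13% is about 15% of the no-adjustment decisions (13/86).

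**Conclusion.** The point holds. SAP 10.1 defines CP for a normal-Z CHW test and plans a test that uses Fisher-based Z whenever a cell is 5 or fewer. Where that branch applies and the effect favours CINRYZE, the stated CP is too high. In the four tables shown it is about two to three times the planned test's CP at n2 = 15, and the stated n2* leaves that CP at 31–44% instead of 60%. The overstatement is not universal, as the exceptions show.

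The result rests on balanced arms of 15, α = 0.0249 in the CP and a one-sided Fisher p; none of the three is what produces the gap. CHW type I error is not affected, because the weights are fixed. The stop is not called into question: for a positive effect on the Fisher branch, correction lowers CP and raises n2*. The text should still be corrected, because it states a decision threshold and a sample size rule that do not fit the planned test.

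**What to change.** 1. Take Z1 in the CP from the statistic that the test uses, Fisher-based when any stage 1 cell is 5 or fewer. Obtain CP and n2* by enumerating stage 2 tables under the switching rule. Putting the Fisher Z1 into the existing formula is a useful check only, since it can fall short at small n2.
2. State α = 0.0249 in the CP and the side of the Fisher p-value.
3. Reconcile the switching rule with the table that names Fisher's exact test alone. The choice changes n2*: Fisher at both stages would need 32, 28, 49 and about 60–62 per arm for 8 v 4, 7 v 3, 5 v 2 and 6 v 3.
4. Check the second line of the CP formula on the original page. If it is printed as extracted, replace it with 1 − Φ[(Z₁₋α − w1·Z1)/w2 − Δ/√(2P(1−P)/n2)].
5. Establish which formula the DMC SAP and the interim code used, and correct any CP or n2* that is reported.

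The cost is wording in the SAP and DMC SAP and a few lines of code. No patients are needed.

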## **15. DATA MONITORING/REVIEW COMMITTEE**

An independent Data Monitoring Committee (DMC) will be established to assess safety, efficacy, and futility during the study, as well as to ensure the validity and scientific merit of the trial. The DMC data review meetings will be held after each interim analysis to review the accumulating safety and efficacy data. Additionally, the DMC will review the safety data approximately every 6 months for the duration of the study.

The roles, responsibilities and rules governing operation of the DMC are discussed in full in the DMC charter v3.0 dated 06 March 2019, which will be finalized prior to the administration of investigational product. The DMC charter will define the primary responsibilities of the DMC; guide its activities, its relationship with other study components, its membership, and the purpose and timings of its meetings. It will provide the procedures for ensuring confidentiality, formal communication, and outline of the content of reports that will be provided to the DMC for each interim analysis. The p-values, conditional power, summary statistics, and data listings will be provided to the DMC by an independent statistician supported by an independent statistical reporting group not otherwise assigned to the study. The statistical analysis details for DMC are discussed in full in the DMC SAP v3.0 dated 06 March 2019.

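### SAP 10.1: as extracted, the second line of the conditional-power formula divides the stage 2 drift by w2, contradicting the first line, so it overstates CP for any positive trend and halves the solved stage 2 size

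*SAP*

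**What the plan says.** SAP Section 10.1 writes CP first as "CP = P\left(Z_2 > \frac{Z_{1-\alpha} - w_1 Z_1}{w_2" and then, as extracted, as "1 - \Phi \left( \frac{Z_{1-\alpha} - w_1 Z_1 - \frac{\Delta}{\sqrt{\frac{2\bar{P}(1-\bar{P})}{n_2}}}}{w_2". It sets both weights to the square root of 1/2 and assumes that the observed trend continues. The final statistic (Formulae 1) is "Z_{CHW} = \sqrt{\frac{15}{30}}Z_1 + \sqrt{\frac{15}{30}}Z_2".

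CP evaluated at 15 per arm in stage 2 drives three decisions. Below a lower limit CPmin the study stops for futility. Between CPmin and 60%, "the sample size will be adjusted up to make CP equal to 60" per cent. At 60% or more, the "study will continue without sample size adjustment".

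The same section fixes the form of each stage's Z: "If the number of TG events exceeds 5 for all four cells in the contingency table of treatment versus TG event", the normal approximation is used; otherwise Z comes from the Fisher exact p-value.

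Section 14 says "The details for calculating CP can be found in" Section 10.1. Section 15 adds: "The statistical analysis details for DMC are discussed in full in the DMC SAP v3.0 dated 06 March 2019". Section 17 reports that the first interim has taken place and that the sponsor stopped the study for futility.

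**The concern.** The second line should only evaluate the first. Z2 is a standardised statistic with unit variance. Under the observed trend its mean is the drift, Delta/sqrt(2P(1-P)/n2), where P is the pooled proportion. The drift therefore has to be subtracted after the division by w2, or carry a factor w2 inside the numerator. As extracted, line 2 does neither, and dividing the drift by 0.7071 multiplies it by 1.414.

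At stake is the quantity that separates stopping, enlarging and continuing. An overstated CP makes a weak positive trend look more promising than it is and returns too small a stage 2 size. Section 17 gives the size of the required increase as a reason for stopping, so the formula is also part of the record of that decision.

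**Working it through.** **Inputs.** w1 = w2 = 0.7071; stage 1 and planned stage 2 of 15 per arm; final one-sided level 0.0249, so c = 1.9617; CP target 60%, with normal quantile 0.2533 (all SAP 10.1). The SAP gives no worked CP value to reproduce. Its nearest figure, 30 per arm for at least 90% power at 50% v 10% (SAP 2.5), does reproduce: 91.4% by Fisher's exact test and 94.3% by normal approximation.

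**The two expressions**, with d the drift at n2:
- Line 1, with Z2 normal with mean d and variance 1: CP = 1 - Phi((c - w1 Z1)/w2 - d)
- Line 2 as extracted: CP = 1 - Phi((c - w1 Z1 - d)/w2)

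**Why the solved size halves.** For CP = 60% the argument of Phi must equal -0.2533.
- Line 1 needs d = (c - w1 Z1)/w2 + 0.2533.
- Line 2 needs d = c - w1 Z1 + 0.2533 w2, which is w2 times the line 1 value.

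Since d grows with the square root of n2, the ratio of solved sizes is w2 squared = 0.5, whichever form of Z1 is used.

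**Example A: 9/15 placebo v 6/15 CINRYZE.** All four cells exceed 5, so Z1 is the pooled statistic.
- Delta = 0.2, P = 0.5, standard error = sqrt(2 × 0.25/15) = 0.1826, so d = Z1 = 1.0954.
- c - w1 Z1 = 1.9617 - 0.7746 = 1.1871.
- Line 2: (1.1871 - 1.0954)/0.7071 = 0.130, CP = 44.8%.
- Line 1: 1.6788 - 1.0954 = 0.583, CP = 28.0%.
- Size for 60%: line 2, 15 × (1.3662/1.0954)² = 23.3, so 24 per arm. Line 1, 15 × (1.9321/1.0954)² = 46.7, so 47 per arm.

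**Example B: 8/15 v 4/15.** One cell is below 5, so Z1 comes from Fisher's test: one-sided p = 0.1318, Z1 = 1.118.
- Delta = 0.2667, P = 0.4, standard error = 0.1789, d = 1.4907.
- c - w1 Z1 = 1.9617 - 0.7906 = 1.1711.
- Line 2: (1.1711 - 1.4907)/0.7071 = -0.452, CP = 67.4%, so the study stays at 15 per arm (solved size 12.3, below the floor).
- Line 1: 1.6562 - 1.4907 = 0.165, CP = 43.4%, which requires 24.6, so 25 per arm.

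**At the threshold.** Treating Z1 as continuous and pooled, line 2 reaches 60% at Z1 = 1.254, where line 1 gives 39.5%; simulating the weighted statistic directly also gives 39.5%. No 15 v 15 table produces that Z1, so this pairing is only an illustration.

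**Zero or negative trend.** Over all such 15 v 15 tables, CP at n2 = 15 is at most 0.28% under either line, with pooled or Fisher-based Z1.

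**The case against.** **It may be a reading fault.** The evidence is the reach of one fraction bar in a converted PDF. Line 1 and Formulae 1 are both right, and elsewhere in Section 10.1 the subscript of the critical value is visibly garbled. A correct expression with the drift set beside the fraction could have been merged into it. This stands as a reason to look at the page first. Nothing in the documents shows that the bar was misread.

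**The programmed formula is not visible.** Section 17 ties the interim analyses to DMC SAP v3.0 of 06 March 2019, which is not available here. This also stands: the documents do not show that line 2 was ever run.

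**The case of wrongly staying at 15 per arm did not occur if line 2 was used.** Section 17 describes four analyses. Three pointed to a very large increase and one led to a futility recommendation; none kept the planned size. Before the interim, with the SAP's rule for choosing Z, the chance of that case was about 9% at 50% v 10% and about 14% at an assumed 50% v 30%. With pooled Z throughout, ten tables fall there, and eight of them need only 16 to 18 per arm.

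**A reader might infer that the study was stopped on a faulty calculation and that the stop is unsafe.** The documents do not support that. If line 1 was programmed there was no error. If line 2 was programmed, correcting it for a positive trend lowers CP and raises the required size, so a very large increase becomes larger and a futility result stays one. With a zero or negative trend CP is near zero under both lines.

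**Conclusion.** The contradiction is real on the extracted text: line 2 does not follow from line 1 or from the planned test statistic. For any positive trend it overstates CP and halves the solved stage 2 size; the halving applies before rounding and before the floor of 15 per arm. On attainable tables the gap is 44.8% v 28.0% at 9/15 v 6/15 and 67.4% v 43.4% at 8/15 v 4/15.

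A reader might take 60% v 39.5% as the typical size of the error, but that pairing matches no possible interim table.

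Type I error is unaffected, because the weights stay fixed whatever the second-stage size. The study has stopped and the reported results exclude a reversal, so the point is **minor**. It bears on the accuracy of the documented method and of any CP or stage 2 size that is reported. The figures assume level 0.0249 and 15 per arm at stage 1. Two things are unverified: the layout on the original page and the expression actually programmed. The documents give no observed Z1, CP, required size or CPmin, so the actual interim values cannot be recomputed.

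**What to change.** 1. Check the fraction bar in line 2 against the original SAP page. If the drift stands outside the division by w2, the point closes.
2. If it is as extracted, replace line 2 by CP = 1 - Phi((Z at 1-0.0249 - w1 Z1)/w2 - Delta/sqrt(2P(1-P)/n2)).
3. Check which expression was programmed for the first interim under DMC SAP v3.0. Only if it was the printed one, correct any CP or stage 2 size reported in the abbreviated CSR.

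The cost is one look at a page, one corrected line and one check of a program, plus a short recalculation by the SAP's own method if the printed line was used. Alpha and the final test do not change.
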